5.3.1.1. Pharmacokinetic Concentrations

Concentrations Below the Limit of Quantification

For all calculations, figures and estimation of individual pharmacokinetic parameters, all concentrations assayed as below the level of quantification (BLQ) will be set to zero. In log-linear plots these values will not be represented. The BLQ values will be excluded from calculations of geometric means and their CIs. A statement similar to 'All values reported as BLQ have been replaced with zero' should be included as a footnote to the appropriate tables and figures.

Deviations, Missing Concentrations and Anomalous Values

In summary tables and plots of median profiles, concentrations will be set to missing if one of the following cases is true:

1. A concentration has been reported as ND (ie, not done) or NS (ie, no sample);
2. A deviation in sampling time is of sufficient concern or a concentration has been flagged as anomalous by the clinical pharmacologist.

Summary statistics will not be presented at a particular time point if more than 50% of the data are missing. For analysis of pharmacokinetic concentrations, no values will be imputed for missing data.

5.3.1.2. Pharmacokinetic Parameters

Whether actual or nominal PK sampling time will be used for the derivation of PK parameters will be determined by the results of interim PK analyses. If a PK parameter cannot be derived from a patient's concentration data, the parameter will be coded as NC (ie, not calculated). NC values will not be generated beyond the day that a patient discontinues.

In summary tables, statistics will be calculated by setting NC values to missing. Statistics will not be presented for a particular treatment if more than 50% of the data are NC. For statistical analyses (ie, analysis of variance), PK parameters coded as NC will also be set to missing.

If an individual patient has a known biased estimate of a PK parameter (due for example to a deviation from the assigned dose level), this will be footnoted in summary tables and will not be included in the calculation of summary statistics or statistical analyses.

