7.3.1. Blood for PK analysis of PF-05082566

Blood samples (2 mL whole blood at each time point) will be collected for PK analysis of PF-05082566 as outlined in the SOA [Table 2](#) and reported herewith below:

- **Patients in dose-finding cohorts:**
 - Cycles 1- 4 on Day 1 at pre-dose and at the end of PF-05082566 infusion;
 - Cycle 5 on Day 1 at pre-dose, at the end of PF-05082566 infusion, at 2, 6, 168 hrs. (Day 8) and 336 hrs. (Day 15) after the start of PF-05082566 infusion;
 - Predose on Day 1 of Cycles 8, 12, 16, 20 and 24;
 - EOT.
- **Patients in expansion cohorts:** The same PK schedule foreseen in the dose-finding portion will be followed for at least 10 patients in total from all expansion cohorts.

For all other patients (all expansion cohorts), blood for PK will be taken:

- Cycle 1, on Day 1 at pre-dose and at the end of PF-05082566 infusion;
- Predose on Day 1 of Cycles 3, 5, 8, 12, 16, 20, and 24;
- EOT.

PK sampling schedule may be modified based on emerging safety/PK data.

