7.3.2. Blood for PK analysis of Mogamulizumab

Blood samples (3 mL whole blood at each time point) will be collected for PK analysis of mogamulizumab as outlined in the SOA ([Table 2](#)) and reported herewith below:

- **Patients in dose-finding cohorts:**

- Cycle 1:
 - a. On Days 1, 8, 15 and 22 at pre-dose, at the end of mogamulizumab infusion,
- Cycles 2, 3 and 4: at pre-dose;
- Cycle 5:
 - a. On Day 1 at pre dose, at the end of mogamulizumab infusion, and at 6 hrs., and 168 hrs. (Day 8) after the start of the mogamulizumab infusion;
 - b. On Day 15 at pre-dose.
- Pre-dose on Day 1 of Cycles 8, 12, 16, 20 and 24;
- EOT.

[figure not shown]
- **Patients in expansion cohorts:** The same PK schedule foreseen in the dose-finding portion will be followed for at least 10 patients in total from all expansion cohorts.

For all other patients in expansion cohorts, blood for PK will be taken:

[figure not shown]
[figure not shown]
- Cycle 1 on Day 1 at pre-dose and at the end of mogamulizumab infusion;
- Predose on Day 1 of Cycles 3, 5, 8, 12, 16, 20 and 24;
- EOT.

PK sampling schedule may be modified based on emerging safety/PK data.

CCI

CCI

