3.2.3. Pharmacokinetic Endpoints

- PK parameters of PF-05082566 and mogamulizumab, including but not limited to C_{max} , C_{trough} , T_{max} , AUC_{0-last} , AUC_{tau} , $t_{1/2}$, CL and V_{ss} , as data permits.

PK parameters will be determined from serum concentration-time data for Cycle 5 as shown in the following table:

Table 2. PK Parameters to be Determined for PF-05082566 and Mogamulizumab

Parameter	Definition	Method of Determination
AUC_{0-last}	Area under the serum concentration-time profile from time zero to the time of the last measurable concentration (C_{last})	Linear/Log trapezoidal method
AUC_{tau}	Area under the serum concentration-time over dosing interval τ	Linear/Log trapezoidal method
C_{max}	Maximum observed serum concentration	Observed directly from data
T_{max}	Time to first occurrence of C_{max}	Observed directly from data
$t_{1/2}^a$	Terminal half-life	$\log_e(2)/k_{el}$, where k_{el} is the terminal phase rate constant calculated by a linear regression of the log-linear concentration-time curve. Only those data points judged to describe the terminal log-linear decline were used in the regression.
C_{trough}	Predose concentration during multiple dosing	Observed directly from data
CL	Clearance	Dose / $AUC\tau$ for steady state

Parameter	Definition	Method of Determination
V_{ss}^a	Steady-state volume of distribution	$CL * MRT$ where MRT is mean residence time.
$AUC_{0_last}(dn)$	Dose normalized AUC_{last}	$AUC_{0_last} / Dose$
$AUC_{tau}(dn)$	Dose normalized AUC_{tau}	$AUC_{tau} / Dose$
$C_{max}(dn)$	Dose normalized C_{max}	$C_{max} / Dose$

^a If data permit

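### The 50% NC rule in SAP 5.3.1.2 counts PK parameters that were never scheduled as failed derivations, and could remove PK summaries at the expansion dose

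*SAP*

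**What the plan says.** **Suppression rule.** SAP 5.3.1.2 assigns NC to any parameter that a patient's concentrations do not support, and then states: "Statistics will not be presented for a particular treatment if more than 50% of the data are NC". Its one limit on creating NC values concerns time after discontinuation: "NC values will not be generated beyond the day that a patient discontinues".

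**Cycle used.** SAP 3.2.3: "PK parameters will be determined from serum concentration-time data for Cycle 5".

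**Sampling.** Protocol 7.3.1, on expansion: "The same PK schedule foreseen in the dose-finding portion will be followed for at least 10 patients in total from all expansion cohorts". Protocol 7.3.2 has the same provision for mogamulizumab. The full Cycle 5 schedule has six time points for PF-05082566 (pre-dose, end of infusion, 2, 6, 168 and 336 hours) and five for mogamulizumab (pre-dose, end of infusion, 6 and 168 hours, and Day 15 pre-dose). The remaining expansion patients have a sparse schedule. After Cycle 1, and apart from the end-of-treatment sample, it is "Predose on Day 1 of Cycles 3, 5, 8, 12, 16, 20, and 24" for PF-05082566, with the same cycles for mogamulizumab. That is one Cycle 5 sample per drug.

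**Who is counted and how.** SAP 4.3.2 admits to the PK parameter set any patient with at least one parameter of interest. SAP 5.2 summarises PK by treatment group, and treatment groups are dose levels (SAP 3.4.1), with no split by study portion or sampling schedule. SAP 6.2.3 plans to list and summarise the Cycle 5 parameters by dose.

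**The concern.** A single Cycle 5 trough supports Ctrough. It cannot give AUC0-last, AUCtau, Tmax, t1/2, CL or Vss. A sparse-schedule patient who reaches Cycle 5 therefore enters the PK parameter set through Ctrough and, on the text as written, carries NC for the other parameters. The rule makes no distinction between a profile that was collected but could not be analysed and one that was never planned.

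A 50% threshold is normally there to keep poorly supported summaries out of the tables. Here it could work the other way. A dose level with three fully sampled patients and no sparse ones would be tabulated. The expansion dose, with up to 19 fully sampled patients (10 expansion plus 9 dose-finding), might not be. PK of the two drugs in combination is a secondary objective, and further PK/PD study is one stated purpose of expansion.

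**Working it through.** The documents give no expected NC percentage, so there is no stated figure to reproduce.

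**Inputs**
- N, expansion patients at the dose: up to 40 in total (SAP 2.2).
- R, expansion patients on the full schedule: at least 10 in total (Protocol 7.3.1 and 7.3.2).
- m, dose-finding patients at the same dose, all on the full schedule: 3 to 9 per cohort (Protocol 3.1.9); m = 0 is added as a bound.
- Threshold: more than 50% NC (SAP 5.3.1.2).

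**Expected NC share** = (N − R)/(N + m), taking every full profile as derivable.

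| m | N = 40, R = 10 | N = 30, R = 10 |
|---|---|---|
| 0 | 30/40 = 75% | 20/30 = 67% |
| 3 | 30/43 = 70% | 20/33 = 61% |
| 6 | 30/46 = 65% | 20/36 = 56% |
| 9 | 30/49 = 61% | 20/39 = 51% |

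If some full profiles also fail, the share rises. With m = 9, N = 40 and 80% of the 19 derivable, it is 1 − 0.8 × 19/49 = 69%.

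**Where the rule stops firing** (share at or below 50%)
- R = 10: N ≤ 20, 23, 26 or 29 for m = 0, 3, 6 or 9. For example, (29 − 10)/(29 + 9) = 19/38 = 50%.
- N = 40: R ≥ 20, 19, 17 or 16 for m = 0, 3, 6 or 9. For example, (40 − 16)/(40 + 9) = 24/49 = 49%.

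**Drop-out before Cycle 5.** Patients who leave earlier generate no NC value, so the counts that matter are those still on treatment in Cycle 5. If retention r does not depend on sampling schedule, the expected share is about unchanged, but the realised share varies. The documents give no retention figure, so r is an assumption. With fully sampled X ~ Bin(R + m, r) and sparse Y ~ Bin(N − R, r), suppression occurs when Y > X:

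| Case | r = 0.1 | r = 0.2 | r = 0.5 |
|---|---|---|---|
| N = 40, m = 0 (30 sparse, 10 full) | 0.79 | 0.92 | >0.99 |
| N = 40, m = 6 (30 sparse, 16 full) | 0.67 | 0.80 | 0.97 |
| N = 40, m = 9 (30 sparse, 19 full) | 0.61 | 0.73 | 0.92 |
| N = 30, m = 6 (20 sparse, 16 full) | 0.47 | 0.55 | 0.69 |
| N = 30, m = 9 (20 sparse, 19 full) | 0.41 | 0.45 | 0.50 |

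At 40 expansion patients with 10 fully sampled, suppression is the more likely outcome throughout this range. At 30 with 9 dose-finding patients pooled it is a coin flip or less, although the expected share is 51%.

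**With the denominator limited** to patients scheduled for the full profile, the NC share caused by design is 0%.

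**The case against.** The strongest reply is that suppression needs three conditions at once: enrolment near the ceiling, full sampling near the floor, and a single expansion dose. The documents fix none of them. Ten is a minimum and 40 a maximum. Protocol 9.3 leaves the expansion total to emerging data, Protocol 3.4 allows the MTD or lower doses, and the PK schedule may itself be modified. This stands, and it makes the point conditional. If expansion spans several doses, the result depends on where the fully sampled patients fall.

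A reader might infer that the expansion-dose PK would be hidden. The documents do not support that. SAP 6.2.3 keeps individual parameter listings, individual and median Cycle 5 concentration plots and the Ctrough summary, and it allows dose-normalised AUCtau and Cmax plots for PF-05082566. Only tabulated summary statistics are at risk. Nor does any decision rule depend on them: the MTD rests on the DLT model.

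A reader might also infer that Cmax would be reported as the trough for sparse patients, because SAP Table 2 takes Cmax as directly observed. No section says that a lone pre-dose sample will be used this way. If it were, Cmax would not be NC and the rule would not affect it.

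Finally, the rule sits in the missing-data section, parameters are to be derived as data permit, and a sensible analyst could treat unscheduled profiles as outside it. That is a reasonable reading, but the text does not state it. SAP 5.3.1.2 defines NC by whether derivation is possible and exempts only time after discontinuation.

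**Conclusion.** The point holds as a conditional, minor one. On its wording, the 50% rule counts values absent by design as failed derivations. With expansion near 40 at one dose and close to 10 fully sampled, the expected NC share for Cycle 5 AUC, CL, t1/2, Vss and Tmax (and Cmax, unless read from the lone trough) is 61% to 70% with 9 to 3 dose-finding patients pooled, and 75% with none. The rule could then remove these summary statistics at the expansion dose.

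It does not follow that the plan will do so. Suppression is not expected with about 20 to 29 or fewer expansion patients at the dose, or with 16 to 20 or more fully sampled, the exact limit depending on how many dose-finding patients are pooled. Near those limits the outcome turns on chance drop-out. The figures rest on pooling by dose level as SAP 5.2 sets out, retention unrelated to sampling schedule, and all full profiles being derivable.

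**What to change.** In SAP 5.3.1.2, apply the 50% rule only to patients scheduled for the full Cycle 5 profile, meaning the dose-finding patients plus the expansion patients assigned to that schedule. Code the other expansion patients as not scheduled rather than NC, and derive only Ctrough for them in Cycle 5. This also settles how Cmax is handled for sparse patients.

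The cost is one or two sentences and a sampling-schedule flag in the analysis data. No new samples or data are needed.

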5.3.2. Handling of Incomplete Dates

5.3.2.1. Disease History

Incomplete dates for disease history (eg, initial diagnosis date, date of documented, locally advanced, inoperable or metastatic disease diagnosis, date of response or progression in prior treatment) will be imputed as follows:

- If the day is missing, it will be imputed to the 1st day of the month.
- If both day and month are missing, the month and day will be imputed as January 1st.
- If the date is completely missing, no imputation will be performed.

5.3.2.2. Adverse Events

Incomplete AE-related dates will be imputed as follows:

- If only the day part of the AE onset date is missing, then the AE onset date will be replaced by 1st of the month. For example, if the AE onset date is --/JAN/2015, then the imputed AE onset date will be 01/JAN/2015.
- If both the day and month of the AE onset date are missing, then the onset date will be replaced by January 1st of the year. For example, if AE onset date is --/---/2014, then the imputed AE onset date will be 01/JAN/2014. In all other cases the missing onset day or missing onset month will be replaced by 1.
- If after above imputation, the imputed onset date with same month and year of the start of study treatment but less than the start of study treatment, and stop date is not less than the start of study treatment, then the imputed AE onset date will be re-assigned as the start of study treatment.
 - If the AE onset date is missing completely, then the onset date will be imputed as following: If not missing the visit date and visit date is less than the start of study treatment and less than or equal to the stop date, then the visit date will be used to impute the onset date.
 - Else if previous visit date is greater than or equal to the start of study treatment and less than or equal to the stop date, then the previous visit date will be used to impute the onset date.
 - Else if previous visit date is less than the start of study treatment and the start of study treatment is less than or equal to stop date, then the start of study treatment will be used to impute the onset date.
 - Else Stop date will be used to impute the onset date.
- Incomplete stop date will be replaced by the last day of the month (if day is missing only).

- Incomplete stop date will be replaced by the last month of the year (if month is missing).
- If the AE stop date is missing completely and still present, then the stop date will be imputed as following:
 - If not missing death date, then death date will be used to impute the stop date.
 - Else if not missing withdrawal date or Date Decision to Discontinue Treatment, the stop date will be imputed as the maximum of Withdrawal date, Date Decision to Discontinue Treatment, Onset date or AE visit date.
 - Else if missing withdrawal date and Date Decision to Discontinue Treatment, the stop date will be imputed as the maximum of subject summary visit date, Onset date or AE visit date.
 - Else the stop date will be imputed as the maximum of onset date or last dosing date.
- If the AE stop date is missing completely and event resolved, then the stop date will be imputed as following:
 - If visit date is greater than onset date, then the visit date will be used to impute the stop date.
 - Else the onset date will be used to impute the stop date.
- If after above imputation, the imputed stop date is less than the start of study treatment, then the imputed AE stop date will be re-assigned as the start of study treatment.
- In all other cases the incomplete stop date will not be imputed. If stop date of AE is after date of cut-off outcome of AE is ongoing at cut-off.

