3.5. Safety Endpoints

3.5.1. Adverse Events

Treatment-Emergent Adverse Events

Treatment-emergent adverse events (TEAEs) are those events with onset dates occurring during the on-treatment period for the first time, or if the worsening of an event is during the on-treatment period.

On-treatment period is defined as the time from the first dose of study treatment through minimum (30 days + last dose of study treatment, start day of new anti-cancer drug therapy – 1 day). The start day of new anti-cancer drug therapy after the first dose of study treatment is derived as outlined in [Section 5.2.5](#).

Adverse Events of Special Interest (AESIs)

AESIs are immune-related adverse events (irAE) and infusion-related reactions (IRRs). The identification of an AE as an irAE or IRR will be performed by clinical review based on the utomilumab safety review plan (SRP).

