5.2.7. Definition of On-treatment Period

Safety endpoints will be summarized based on the on-treatment period unless otherwise specified.

On-treatment period is defined as the time from the first dose of study treatment through minimum (30 days + last dose of study treatment, start day of new anti-cancer drug therapy – 1 day).

Safety data collected outside the on-treatment period as described above will be listed and flagged in listings but not summarized.

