6.6.1. Adverse Events

Treatment-emergent adverse events (TEAEs) are those events with onset dates occurring during the on-treatment period for the first time, or if the worsening of an event occurs during the on-treatment period as defined in [Section 3.5.1](#).

All analyses described will be based on TEAEs (started during the on-treatment period) if not otherwise specified. The AE listings will include all AEs (whether treatment-emergent or not). AEs outside the on-treatment period will be flagged in the listings.

- **Related Adverse Events:** adverse events with relationship to study treatment (as recorded on the AE eCRF page, Relationship with study treatment = Related) reported by the investigator and those of unknown relationship (ie, no answer to the question 'Relationship with study treatment').
- **Serious Adverse Events (SAE):** serious adverse events (as recorded on the AE eCRF page, Serious Adverse Event = Yes).

- **Adverse Events Leading to Permanent Treatment Discontinuation:** adverse events leading to permanent discontinuation of study treatment (as recorded on the AE eCRF page, Action taken with study treatment = Drug withdrawn).
- **Adverse Events Leading to Death:** adverse event leading to death (as recorded on the AE eCRF page, Outcome = Fatal, as well as AEs of Grade 5).
- **Immune-related Adverse Events (irAE):** irAEs (as identified by clinical review based on the SRP prior to DB lock).
- **Infusion-related Reactions (IRR):** IRRs (as identified by clinical review based on the SRP prior to DB lock) with onset on study drug dosing date (not prior to infusion of study drug) or the day following study drug infusion.

Unless otherwise specified, AEs will be summarized by number and percentage of patients with the AE in the category of interest as described above, by treatment group, primary SOC and PT in decreasing frequency observed in all treatment groups combined.

Each patient will be counted only once within each SOC or PT. If a patient experiences more than one AE within a SOC or PT for the same summary period, only the AE with the strongest relationship or the worst severity, as appropriate, will be included in the summaries of relationship and severity.

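### A year-only AE onset in the calendar year of first dose is imputed to before treatment for every patient first dosed from February to December, and so drops out of the TEAE summaries

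*SAP*

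**What the plan says.** SAP 5.3.2.2 imputes partial AE onset dates. When day and month are both missing, "then the onset date will be replaced by January 1st of the year". Its example is an onset recorded only as 2014: "then the imputed AE onset date will be 01/JAN/2014".

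A safeguard follows. It resets the onset to the start of treatment when the imputed value is "the imputed onset date with same month and year of the start of study treatment but less than the start of study treatment". A further requirement is that the event did not end before first dose. All of these conditions must hold together.

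A completely missing onset has its own sequence of rules based on visit dates. One branch applies when the previous visit was before first dose and the event had not stopped before first dose: "then the start of study treatment will be used to impute the onset date". That branch has no month condition.

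SAP 3.5.1 and 6.6.1 define treatment-emergent events as "those events with onset dates occurring during the on-treatment period for the first time", or events that worsen in that period. SAP 5.2.7 sets its lower limit: "On-treatment period is defined as the time from the first dose of study treatment through minimum" of two end dates. Safety data outside the period are listed with a flag but not summarised. Under SAP 6.6.1, AE analyses use TEAEs unless stated otherwise. Protocol 8.2 has AEs recorded on the CRF from the first dose until the last visit, while SAE reporting to the sponsor starts at consent.

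**The concern.** The safeguard exists so that imputation does not push an on-treatment event back before treatment. It works when only the day is missing, because the month is then a recorded fact and comparing it with the month of first dose makes sense. When the month is missing too, the safeguard compares an invented month, always January, with the real month of first dose. That test fails for every patient who did not start in January, whatever the patient's event was.

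The result also sits badly with the rest of the section. An event with no onset date at all can be assigned to first dose. An event with a known year that agrees with the year of first dose cannot, unless dosing began in January. The SAP gives no reason for protecting the better-documented date less. Because the CRF collects AEs from first dose onward, a year-only onset in the dosing year is more likely to be post-dose than pre-dose, so the imputed date will usually be wrong.

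At stake are the TEAE tables, including those for related, serious and Grade 3 or higher events. An affected event would be missing from its dose group's counts.

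**Working it through.** **Inputs.** Imputation and safeguard: SAP 5.3.2.2. TEAE definition: SAP 3.5.1 and 6.6.1. Start of the on-treatment period: SAP 5.2.7. Treatment of up to 24 months: Protocol 5.4.4. Dose-finding cohorts of 3 to 9 evaluable patients: Protocol 3.1.9. Up to 40 expansion patients: SAP 2.2.

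**Step 1: reproduce the SAP's example.** Recorded year 2014, missing day and month set to 1, gives 01 January 2014, as the SAP states.

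**Step 2: apply the full rule to cases.** The stop date is taken as 10 days after true onset, so it is always after first dose.

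| First dose | True onset | Recorded | Onset after the SAP rule | Class |
|---|---|---|---|---|
| 15 Jun 2016 | 10 Aug 2016 | 2016 | 1 Jan 2016 (no month match) | pre-treatment |
| 2 Feb 2016 | 20 Feb 2016 | 2016 | 1 Jan 2016 (no month match) | pre-treatment |
| 20 Jan 2016 | 1 Mar 2016 | 2016 | 20 Jan 2016 (safeguard applies) | on-treatment |
| 15 Oct 2015 | 1 Feb 2016 | 2016 | 1 Jan 2016 (already after first dose) | on-treatment |
| 20 Dec 2016 | 10 Jan 2017 | 2017 | 1 Jan 2017 (already after first dose) | on-treatment |

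**Step 3: generalise.**
- Onset year equals first-dose year, first dose 1 February to 31 December: 1 January is always earlier than first dose and the month never matches. All such onsets (100%) are pre-treatment.
- Same year, first dose in January, stop date not before first dose: none (0%).
- Onset year later than first-dose year: 1 January of that year is after first dose. None (0%), whatever the month of dosing.

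**Step 4: share of year-only, post-dose onsets affected, for patients not dosed in January.** Assumptions, not in the documents: first-dose dates spread evenly over the 334 days from February to December, and true onset spread evenly over the first W days from first dose. Let r be the number of days left in the year after first dose. The onset falls in the next year or later on W − 1 − r of the W days when that is positive. The unaffected share is the sum of those counts over r = 0 to 333, divided by 334 × W.

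| W (days) | Unaffected | Classed pre-treatment |
|---|---|---|
| 56 | 1,540 / 18,704 = 8.2% | 92% |
| 112 | 6,216 / 37,408 = 16.6% | 83% |
| 365 | 65,965 / 121,910 = 54.1% | 46% |
| 730 | 187,875 / 243,820 = 77.1% | 23% |

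These are shares of year-only dates, not of all AEs. The gap matters most early in treatment.

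**Step 5: effect on an incidence.** One patient removed from a category is 1/9 = 11% to 1/3 = 33% of a dose-finding cohort. If all 40 expansion patients joined a 9-patient dose level, it would be 1/49 = 2%.

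**The case against.** **Such dates should be rare.** This largely stands. AEs are recorded at each visit, the schedule has weekly visits in Cycles 1 and 2, SAEs are reported within 24 hours of awareness, and the analysis uses cleaned data. An onset with neither day nor month will be unusual, and the commoner gap, a missing day, is already covered by the safeguard. The documents give no count. Rarity limits the impact but does not make the rule correct.

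**Nothing disappears from the record.** This also stands. All AEs are listed, those outside the on-treatment period and imputed values are flagged, and recorded worsening on treatment still makes an event a TEAE. The summaries are nevertheless what most readers use.

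**The 11 to 33 points is an upper bound.** Agreed. A patient is counted once per SOC or preferred term, so a lost event changes an incidence only if that patient has no other qualifying event in the category. Treatment groups are defined by dose level, so expansion patients can dilute the effect.

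A reader might also draw three stronger conclusions that the documents do not support:
- *Every year-only onset is lost unless dosing began in January.* No. Onsets in a later calendar year are imputed after first dose, and treatment can run for 24 months.
- *The imputation can only remove events.* No. The on-treatment period ends 30 days after last dose, or the day before new anti-cancer drug therapy if earlier. Take a patient first dosed in an earlier year whose last dose was in mid-January. A true June onset recorded only by year would be imputed to 1 January and counted as treatment-emergent. The errors of 1 January imputation therefore do not all run one way.
- *The primary endpoint is affected.* Nothing says that DLT status is derived from imputed dates. Under Protocol 3.1.9, DLT data go to the study statistician as the trial proceeds.

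**Conclusion.** The point holds within stated limits. Followed exactly, SAP 5.3.2.2 classes a year-only onset in the year of first dose as pre-treatment for every patient first dosed from February to December, even when the stop date is on or after first dose. The event then leaves the TEAE summaries unless on-treatment worsening is recorded. This follows from the SAP's own text and needs no outside convention.

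The effect is at most 11 to 33 percentage points per event in a dose-finding cohort of 3 to 9, and smaller in larger groups. How often it happens cannot be determined from the documents and is probably seldom. The percentages by onset window depend on the even-spread assumptions; the February-to-December result does not. It is a small defect with a cheap cure, and it should be corrected.

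**What to change.** Apply the safeguard to the recorded parts of the onset date instead of the imputed date. If the recorded year (or the recorded month and year) equals that of first dose, the imputed onset is before first dose, and the stop date is missing or not before first dose, set onset to the date of first dose.

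With this rule the first case in the working becomes 15 June 2016 instead of 1 January 2016, and the 92%, 83%, 46% and 23% all become 0%. Onsets in a later year are unchanged. The rule also covers a date on which only the month is missing; the SAP sets that month to January too, so it has the same gap.

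The cost is one sentence in the SAP and a small code change. The downside is that a few truly pre-dose events may be counted as TEAEs, for example SAEs between consent and first dose with a year-only onset. The change does not address the opposite error, a post-treatment onset pulled back into the on-treatment period.
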